3.7.1.1 AE Bothersome Survey

Investigators will ask subjects about the prostanoid-related effects they experienced using the AE Bothersome Survey. For this study, adverse events of interest include headache, diarrhea, nausea, flushing, jaw pain, extremity pain, and vomiting. The survey is provided in protocol Appendix E. The number and percentage of subjects reporting each of the adverse events of

interest at Baseline, the Transition Visit, and Week 16/Early Study Withdrawal will be provided (Question 1).

For each symptom (headache, diarrhea, nausea, flushing, jaw pain, extremity pain, and vomiting), AE Bothersome Survey scores will be summarized at Baseline, the Transition Visit, and Week 16/Early Study Withdrawal for each question (Question 2, and Question 3). In addition, change from Baseline and change from Transition Visit will be provided. For each symptom, the following scoring system will be utilized and an overall Burden Score will be provided:

	1 day	2 days	3 days	4 days	5 days	6 days	7 days
Not at all	0	0	0	0	0	0	0
Bothers me a little	3	4	5	6	7	8	9
Bothers me some	5	6	7	8	9	10	11
Bothers me a lot	8	9	10	11	12	13	14

Points	Burden Score
0	Not at all burdensome
3 to 6	Mildly burdensome
7 to 9	Moderately burdensome
10 to 14	Very burdensome

3.7.2 Vital Signs and Clinical Laboratory Tests

Vital signs and clinical laboratory tests will not be listed or summarized.

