10.3.3 Safety Analyses

The Safety Population will be defined as all subjects in the study that receive study drug. All safety analyses will be performed on the Safety Population. Safety will be evaluated by assessment of AEs, clinical laboratory evaluations, and vital signs. All AEs as recorded by the Investigators will be assigned Medical Dictionary for Regulatory Activities (MedDRA) Preferred Terms by the Sponsor for reporting purposes. For all safety endpoints, tabular summaries will be provided.

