10.6 DATA LISTINGS AND SUMMARIES

All data gathered in this study will be presented in summary tables and listings in the final clinical study report. In general, listings will be sorted by subject and scheduled assessment (if applicable). For summary tables, data will be summarized by scheduled assessment. For continuous variables, descriptive statistics will include the number of observations, mean, SD, median, inter-quartile range, minimum, and maximum. For categorical variables, descriptive statistics will include the frequency and percent in each category.

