2.3.2 Secondary Endpoints

2.3.2.1 Safety Endpoints

Safety will be assessed using the Prostanoid Adverse Event (AE) scores captured by the AE Bothersome Survey at Baseline, the Transition Visit, and Week 16/Early Study Withdrawal.

The Investigator will administer the AE Bothersome Survey (provided in protocol Appendix E) at time points listed in Table 1 to collect information about prostanoid-related effects experienced by the subject, including headache, diarrhea, nausea, flushing, jaw pain, extremity pain and vomiting. For each prostanoid-related effect, whether the patient has experienced the effect, the degree of bothersome (from 1 - bothers me a lot to 4 - not at all bothersome), and days experiencing it (1 to 7) will be recorded.

Other safety assessments including the incidence of adverse events, clinical laboratory tests, vital signs, and physical examinations are described in Section 3.7.

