3.1.5 Summary Statistics

The efficacy and safety data in the study will be presented in summary tables and listings in the final clinical study report. Listings will be sorted by subject, visit, and time point assessment (if applicable). For summary tables, the data will be summarized by visits (including the Transition Visit) and time point assessment, if appropriate. For continuous variables in general, descriptive statistics will include the number of observations (non-missing values), mean, standard deviation (SD), median, inter-quartile range, minimum, and maximum. Change from Baseline will also be provided if applicable. For categorical variables, descriptive statistics will include the frequency and percentage in every category.

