3.7 Safety Assessment

Safety data will be summarized based on the Safety Population.

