6 PROGRAMMING SPECIFICATIONS

Analyses will be performed using SAS® version 9.3 or higher. All available data will be presented in subject data listings which will be sorted by subject and visit date as applicable. Detailed Programming Specifications will be provided in a separate document.

REFERENCE

[1] Boucly, Athénaïs, et al. "Risk assessment, prognosis and guideline implementation in pulmonary arterial hypertension." European Respiratory Journal 50.2 (2017).

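### SAP 3.7.2 drops all reporting of vital signs and laboratory tests, against the protocol and the SAP's own general rules, and SAP 5 does not declare it

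*SAP*

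**What the plan says.** SAP 3.7.2 consists of one sentence: "Vital signs and clinical laboratory tests will not be listed or summarized".

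Other sections say the opposite:

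- Protocol 10.3.3: "Safety will be evaluated by assessment of AEs, clinical laboratory evaluations, and vital signs". The same section adds: "For all safety endpoints, tabular summaries will be provided".
- Protocol 10.6: "All data gathered in this study will be presented in summary tables and listings in the final clinical study report".
- SAP 3.1.5: "The efficacy and safety data in the study will be presented in summary tables and listings in the final clinical study report".
- SAP 3.7, the parent section of 3.7.2: "Safety data will be summarized based on the Safety Population".
- SAP 6: "All available data will be presented in subject data listings which will be sorted by subject and visit date as applicable".
- SAP 2.3.2.1 sends the reader forward: "Other safety assessments including the incidence of adverse events, clinical laboratory tests, vital signs, and physical examinations are described in Section 3.7".

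SAP 5, where changes from the protocol's analyses are to be recorded, has two entries: an informal interim analysis for publication, and an increase to about 35 evaluable subjects.

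**The concern.** Safety and tolerability are a stated secondary objective. The plan schedules vital signs at every visit and chemistry and hematology at four time points, then says the results will not be shown. No reason is given and the departure from the protocol is not declared. SAP 1 does not close the gap: it asks the study report to document deviations from the SAP, and a team that follows 3.7.2 has not deviated from the SAP. Nothing in the plan would therefore require disclosure.

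At stake are changes that no investigator reports as an adverse event. Protocol 1.2.1 describes treprostinil as dilating systemic as well as pulmonary vessels and as inhibiting platelet aggregation, and Protocol 6.1 sets no maximum dose for either product. A modest shift across the group in blood pressure, heart rate, platelets or hemoglobin, with no individual change judged clinically significant, would not appear as a safety result. The interim analysis in SAP 4.1 has the same gap. It is meant to compare the safety profile with historical transition data, but its output list contains no on-treatment vital signs, chemistry or hematology.

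**Working it through.** The plan gives no figure to reproduce here. The check has three parts.

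**1. Do the sections conflict?**

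| Section | Commitment | Compatible with SAP 3.7.2? |
|---|---|---|
| Protocol 10.3.3 | Three safety components; tables for safety endpoints | No |
| Protocol 10.6 | Tables and listings of all data | No |
| SAP 3.1.5 | Tables and listings of safety data | No |
| SAP 3.7 | Safety data summarized | No, though the sentence mainly names the population |
| SAP 6 | Listings of all available data | No, as to listings |
| SAP 2.3.2.1 | Points to 3.7 for laboratory tests, vital signs and physical examinations | For the first two, 3.7 offers only the removal; physical examinations are not covered there at all |

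Of the three components in Protocol 10.3.3, adverse events are covered by SAP 3.7.1 and the other two are removed: 2 of 3. Of the four items under the safety objective in the protocol synopsis (adverse events, AE Bothersome Survey, laboratory parameters, vital signs), 2 of 4 are removed. SAP 5 lists two changes, neither of them this one.

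**2. Do the data reach the report another way?**

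- Height, weight and BMI: Baseline only (SAP 3.3.4).
- Heart rate and systemic pressures from right heart catheterization: baseline characteristics (SAP 3.3.4.1).
- Systolic pressure, heart rate and eGFR as scored REVEAL 2.0 components: Baseline only. At the Transition Visit and Week 16 only the composite score is planned, as an exploratory efficacy endpoint (SAP 3.3.4.2).
- Echocardiographic heart rate, heart rate recovery after the walk, and NT-proBNP: efficacy outputs (SAP 2.3.2.2 and 3.4.2).
- Laboratory changes judged clinically significant: reported as adverse events (Protocol 9.1.1 and Appendix C).

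None of these is a by-visit safety summary of vital signs, chemistry or hematology on treatment.

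**3. How much is left out?** Inputs are Protocol Table 3-1 and Appendix D, for a subject who transitions and completes.

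- Vital signs: systolic and diastolic pressure, heart rate, respiration rate and weight = 5 measures (height left out as static). Treatment visits are Weeks 2, 4 and 8, Post Transition, and Weeks 12 and 16 = 6, or 5 if Week 4 serves as the Post Transition Visit. 5 × 6 = 30; 5 × 5 = 25.
- Laboratory: 14 chemistry + 6 hematology tests (CD4 excluded) at the Transition Visit and Week 16. 20 × 2 = 40.
- Per subject: 25 + 40 = 65 to 30 + 40 = 70.
- Over 30 evaluable subjects (Protocol 3.5) to 35 (SAP 2.2.3): 30 × 65 = 1,950 to 35 × 70 = 2,450.

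The total assumes that every evaluable subject transitions. A completer who stays on Remodulin has five treatment visits and one on-treatment laboratory draw: 25 + 20 = 45 values. Even if none of 30 transitioned, the count would be 30 × 45 = 1,350.

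**The case against.** The strongest points on the other side, and what remains of each:

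- **Protocol 10.3.3 can be read narrowly.** Its promise of tables concerns safety endpoints, and Protocol 10.3.2.1, headed as such, contains only the prostanoid adverse event scores. SAP 2.3.2.1 also separates that endpoint from other safety assessments. The reading is possible, but it does not touch Protocol 10.6 or SAP 3.1.5, which cover all data and all safety data.
- **SAP 6 may still require listings.** If it prevailed, listings would exist and only the tables would be missing. The natural reading is that the specific sentence governs the general one, but the status of listings is at best contradictory. The tables are missing either way.
- **The protocol leaves details to the SAP.** Protocol 10.3 defers further details. Removing two named safety components reverses a stated analysis; it does not elaborate one.
- **The products are well characterized and adverse event reporting is thorough.** Protocol 1.2.3 says Remodulin has not been associated with significant laboratory changes, which lowers the expected yield of laboratory tables. It does not address vital signs. Adverse event reporting would capture symptomatic hypotension, but not unreported shifts. The SDTM and ADaM datasets in SAP 4.3 would keep the values available, but they are not the tables and listings promised for the report.
- **The value count measures volume, not risk.** This stands. It says nothing about the chance of a missed signal, and the totals are illustrative. The informative size is two of three components.
- **Declaring the omission would cure most of the defect.** This is largely true, and it is why the fix allows that route. As it stands, the omission is neither declared nor reconciled.

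**Conclusion.** The concern holds, and the text must change before the plan is followed. SAP 3.7.2 contradicts Protocol 10.3.3 and 10.6 and SAP 3.1.5 and 6; the conflict with SAP 3.7 is real but weaker. The omission is missing from SAP 5. Following the plan as written leaves two of the three protocol safety components without an on-treatment safety table by visit.

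The further conclusion that listings are also absent rests on 3.7.2 overriding SAP 6. The count of 65 to 70 values applies to a subject who transitions and completes all scheduled visits. The size of any safety signal that could be missed cannot be estimated from the documents. The primary endpoint can still be calculated: it uses the prescribed Orenitram dose and, for subjects under 70 kg, a body weight that is collected whether or not it is tabulated.

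**What to change.** Replace SAP 3.7.2 with the following, for the Safety Population:

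- by-visit descriptive summaries of observed values and change from Baseline for blood pressure, heart rate, respiration rate and weight, and for serum chemistry and hematology;
- change from the Transition Visit for subjects who have one, matching the treatment of efficacy parameters in SAP 3.4.2 (a recommendation, not something the protocol already promises for these data);
- by-subject listings of the same values.

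Shift tables, or counts against the values used as entry criteria in Protocol 4.2, are optional. They should be labelled descriptive, because the protocol does not set those values as on-treatment limits.

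State in SAP 3.7 how physical examinations will be reported, or correct the cross-reference in SAP 2.3.2.1. Decide whether the interim output list in SAP 4.1 should include vital signs and laboratory data, given its stated purpose.

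If the sponsor intends to omit any of these outputs, record the omission and its reason in SAP 5, and align SAP 2.3.2.1, 3.1.5, 3.7 and 6 with it.

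The cost is SAP wording plus a few standard tables and listings. The data are already scheduled in Protocol Table 3-1, so no new assessment is needed.

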4 ANALYSIS TIMING

4.1 Interim Analysis

An interim analysis will be performed when there are about 10 subjects that have conducted the Week 16/ Early Study Withdrawal Visit, to evaluate the safety of Orenitram after induction therapy with Remodulin. The safety profile will be used to check if it is consistent with the historical data on transitions gathered from previous studies.

The following summary tables and listings will be generated for the interim analysis based on the enrolled subjects who have conducted the Week 16/ Early Study Withdrawal Visit:

- Summary of disposition on enrolled subjects as described in section 3.3.1
- Summary of demographic and baseline characteristics will be provided as described in section 3.3.4
- Summary of REVEAL 2.0 risk score as described in section 3.3.5
- Summary of current PAH background medications as described in section 3.3.6
- Summary of study drug exposure (dosage and transition) will be provided as described in section 3.3.7
- The primary and key secondary endpoints (6MWD, Borg dyspnea score, WHO FC and NT-proBNP) will be summarized as described in section 3.4.1 and 3.4.2
- A listing of Remodulin and Orenitram dose levels for each subject at each timepoint will be provided by visit
- Overview summary of AEs as described in section 3.7.1

4.2 Pre-Final Analysis

After the database is locked and exclusions from analysis populations have been finalized, the pre-final analysis will be generated. Pre-final TFLs will be provided approximately 3 weeks after database lock.

4.3 Final Analysis

After all comments on the pre-final analysis have been resolved and the study database is declared final, the final analysis will be generated. Final TFLs will be provided approximately 1 week after the study database is declared final. If there were no changes to the pre-final analysis or the study database, the pre-final TFLs will be considered final. In addition to TFLs, SDTM data and ADaM data along with associated files will be provided. Associated files will include: annotated case report forms (CRFs), reviewer's guide, SDTM specifications, SDTM programs, ADaM specifications, ADaM programs, TFL programs, and Clinical Data Interchange Standards Consortium (CDISC) Define packages for both SDTM and ADaM data.

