10.1.1 EDC

Data will be recorded on the eCRF, and eCRFs will be completed for each subject. Limited data will be recorded on screen failures. Data will be transcribed into an eCRF by the appropriate study site personnel for each subject until study completion, or study discontinuation for any reason. The Sponsor or designee will verify eCRF data fields against source documentation. All data entered in the eCRF by the study site will be entered into a quality assured computerized database. Any discrepancies will be posted in the system for resolution by the site. The eCRF data for every subject is to be reviewed by the Investigator for completeness and accuracy. The Investigator must electronically sign every subject's eCRF to signify their approval of the data. The Investigator will be required to re-sign an eCRF if changes are made to a subject's eCRF by the study site after the Investigator has applied his/her signature. The database will be considered final when all outstanding queries have been resolved and all data management quality assurance procedures are complete.

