3.2.2 Per-protocol Population

The Per-protocol Population is defined as all subjects in the study who received study drug without any major deviations (which may interfere with efficacy evaluation).

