3.3.2 Protocol Deviations

The following listings and summary table will be provided for Safety Population:

- Listing of Entry Criteria.
- Listing of Entry Criteria Violations. The status of the entry criteria will be listed for all subjects. The listing will include the date of the initial screening assessment and a list of any specific entry criteria that were not met.
- Summary of Entry Criteria Violations. If a sufficient number of violations occur, then the compliance to each criterion will be summarized.

Additional protocol deviations not captured in the CRF may be tabulated and listed based on criteria to be determined upon preparation of the final study report.

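### Per-Protocol membership is not required to be fixed before the interim or database lock, nor stated to stay fixed after the pre-final tables, and the major deviations that define it have no listed criteria.

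*SAP*

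**What the plan says.** **Primary set.** SAP 3.4.1 reports the primary percentage on the Per-Protocol Population and repeats it on the Completer Population. A missing Week 16 prescribed dose counts as failure. SAP 3.2.2 gives the definition: "The Per-protocol Population is defined as all subjects in the study who received study drug without any major deviations (which may interfere with efficacy evaluation". No list of such deviations follows. Protocol 10.3 places all efficacy analyses on the Safety Population. SAP 5 does not list the change, and the SAP plans no primary-endpoint summary on that population.

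**Deviations.** SAP 3.3.2 specifies entry-criteria listings and a summary of violations. It adds, with reference to the final report: "Additional protocol deviations not captured in the CRF may be tabulated and listed based on criteria to be determined upon preparation of the final study".

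**Interim.** SAP 4.1 plans tables at about 10 subjects. They include the primary endpoint as described in SAP 3.4.1 and a by-subject, by-visit dose listing. SAP 5 calls the interim informal and intended for publication.

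**Pre-final and final.** SAP 4.2: "After the database is locked and exclusions from analysis populations have been finalized, the pre-final analysis will be generated". SAP 4.3: "After all comments on the pre-final analysis have been resolved and the study database is declared final, the final analysis will be generated". It continues: "If there were no changes to the pre-final analysis or the study database, the pre-final TFLs will be considered final". Protocol 10.1.1 says: "The database will be considered final when all outstanding queries have been resolved and all data management quality assurance procedures are complete".

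**Blinding.** None (Protocol 5.3, SAP 2.2.2).

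**The concern.** The main result is one percentage from a small open-label group. Its numerator is visible to anyone who knows a subject's prescribed dose. Its denominator depends on a judgement for which the SAP gives no criteria.

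Some events could plausibly be handled either way. Protocol 4.3.1 requires withdrawal if another approved PAH treatment is added, Protocol 6.3 allows withdrawal for continued non-adherence, and Protocol 8.1 lists deviation from the protocol as a withdrawal reason. A subject who leaves this way with no Week 16 dose is a failure if kept in the Per-Protocol Population, and disappears from the calculation if classed as a major deviator. The SAP does not say which.

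At stake is the credibility of a descriptive estimate. If classification is settled when outcomes are known, a reader cannot exclude that the outcome influenced it, even when everyone acted in good faith.

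**Working it through.** There is no planned figure to reproduce. SAP 2.2.3 states that no formal sample size computation was done, and the documents give no expected success rate. The check has two parts.

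**1. Order of events**

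| Step | What is fixed | What is left open |
|---|---|---|
| Interim, about 10 subjects (SAP 4.1) | Primary endpoint summarized, doses listed by subject | No sign-off of membership or criteria beforehand |
| SAP finalization (SAP 1) | SAP final before lock | Criteria for a major deviation are not in it |
| Lock and exclusions (SAP 4.2) | Both precede the pre-final tables | Which comes first is not stated |
| Comments on pre-final tables (SAP 4.3) | Database declared final afterwards | Data and analysis may change; no unlock procedure; nothing on whether membership is frozen |

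The interim covers 10/35 = 29% of the SAP's target, or 10/30 = 33% of the protocol's.

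**2. Sensitivity of the percentage**

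Inputs: n = 35 (SAP 2.2.3) and n = 30 (Protocol 10.2). The number of achievers x and the number excluded k are assumptions.

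- Before exclusion: x/n
- After excluding k non-achievers: x/(n − k)
- After excluding k achievers: (x − k)/(n − k)

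For n = 35 and x = 21: 21/35 = 60.0%. Excluding one non-achiever gives 21/34 = 61.8%, three give 21/32 = 65.6%, five give 21/30 = 70.0%. Excluding three achievers gives 18/32 = 56.2%.

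| n | x | Start | 1 non-achiever out | 3 out | 5 out | 3 achievers out |
|---|---|---|---|---|---|---|
| 35 | 18 | 51.4% | 52.9% | 56.2% | 60.0% | 46.9% |
| 35 | 21 | 60.0% | 61.8% | 65.6% | 70.0% | 56.2% |
| 35 | 24 | 68.6% | 70.6% | 75.0% | 80.0% | 65.6% |
| 35 | 28 | 80.0% | 82.4% | 87.5% | 93.3% | 78.1% |
| 30 | 15 | 50.0% | 51.7% | 55.6% | 60.0% | 44.4% |
| 30 | 18 | 60.0% | 62.1% | 66.7% | 72.0% | 55.6% |
| 30 | 21 | 70.0% | 72.4% | 77.8% | 84.0% | 66.7% |
| 30 | 24 | 80.0% | 82.8% | 88.9% | 96.0% | 77.8% |

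The smallest step is 52.9 − 51.4 = 1.5 points. The largest is the fifth exclusion at n = 30, x = 24, from 24/26 = 92.3% to 24/25 = 96.0%, or 3.7 points. Hence about 1.5 to 4 points per excluded non-achiever.

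The SAP's 35 evaluable subjects are already defined as free of major deviations, so subtracting from 35 shows scale only. Run the other way, with an assumed 40 treated and 24 achievers, the figure is 24/40 = 60.0%. If five non-achievers are excluded it is 24/35 = 68.6%, a rise of 8.6 points or 1.7 per subject, inside the same range.

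For comparison, the exact 95% interval for 21/35 is 42.1% to 76.1%. A few exclusions stay inside that width, but an interval describes sampling error and does not show a shift caused by selection.

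**The case against.** The strongest reply is that the SAP already prevents the worst sequence. A reader might infer that exclusions stay open until the tables are seen, so that a low-dose subject could be removed afterwards as part of the plan. SAP 4.2 says otherwise: exclusions are finalized before the pre-final tables are generated. SAP 4.3 speaks of changes to the analysis or the database and does not say that membership reopens. This part of the reply stands. What remains is that SAP 4.2 does not reach back to the interim or the lock, and SAP 4.3 does not say the exclusions hold.

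A reader might also take the criteria left to the report stage in SAP 3.3.2 as the open rule for the primary set. The sentence concerns optional tabulation and listing of extra deviations not captured in the CRF, and the SAP does not link it to Per-Protocol membership. That link would be a guess.

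Nor does SAP 4.3 contradict Protocol 10.1.1. One names the conditions for a final database and the other adds that comments be resolved; both can hold.

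There are safeguards. SAP 1 requires departures from the SAP after lock to be reported in the CSR. SAP 3.3.3 reports counts per population. SAP 3.3.7 lists each subject's doses and summarizes them on the Safety Population, and SAP 6 promises listings of all available data. These would help a reader detect an odd exclusion. They do not close the gap: reclassifying a subject need not depart from a SAP that has no criteria, and no listing of exclusions with reason and endpoint status is specified.

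Finally, exclusions can lower the percentage as well as raise it, and nothing in the documents makes a low dose a deviation. Both are correct.

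**Conclusion.** The concern holds as a gap in timing and definition. Membership of the primary denominator rests on unlisted criteria, need not be settled before the interim or the lock, and is not stated to stay frozen when data or analysis change after the pre-final tables. In an open-label study, that lets exclusions be decided with outcomes known.

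The size is about 1.5 to 4 points per excluded non-achiever, assuming success rates of 50 to 80% and 30 to 35 subjects. Removing achievers moves the figure the other way: from 60.0% to 56.2% for three of 35. The number and direction of any exclusions are unknown.

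SAP 3.1.6 rules out formal testing and no success threshold is set, so the risk is bias in a descriptive percentage, not type I error. The documents show an opportunity; they do not show intent. This is a change that should be made, but the study does not stand or fall on it.

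**What to change.** 1. List the major-deviation criteria in SAP 3.2, including how withdrawal, non-adherence and added PAH therapy are classified for analysis.
2. Decide and sign off Per-Protocol and Completer membership before the final database lock, from a deviation listing without Week 16 dose or efficacy fields. The Completer Population also requires study completion and Orenitram use at Week 16; apply those conditions by program after the deviation decisions are signed.
3. Apply the same criteria to interim subjects before the interim tables. If the interim has already been run, record the classification used then and any change since.
4. Amend SAP 4.3 so that a change to data or membership after the pre-final tables needs a documented unlock, with the primary percentage before and after the change in the CSR.
5. List each excluded subject with the reason and primary-endpoint status.
6. Also report the primary percentage on the Safety Population, as Protocol 10.3 states. This gives an all-treated figure that no deviation decision can alter.

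The cost is SAP wording, one pre-lock review, one listing and one extra table row, with less freedom to revise after the pre-final tables. Removing outcome fields will not make reviewers unaware of doses in an open-label study, so the written criteria carry most of the protection.
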